7.2. Principal Secondary Efficacy Analyses

7.2.1. Endpoint / Variables

[Endpoint / Parameter/ Display Type]	Absolute						
	Stats Analysis			Summary		Individual	
	T	F	L	T	F	F	L
Number (%) of Subjects with Mean Hgb in Target Range during the Primary Efficacy Evaluation Period							
(Principal Secondary) Logistic Regression mITT Population	Y						
Logistic Regression ITT Population	Y						
Logistic Regression PP Population	Y						
Logistic Regression Efficacy ND Population	Y						
Logistic Regression mITT Population By Subgroup	Y	Y ^[1]					
Efficacy PD Population				Y			
Efficacy PD Population By Subgroup ^[2]				Y			

NOTES :

- T = Table, F = Figure, L = Listing, Y = Yes display generated.
- Stats Analysis = Represents TFL related to any formal statistical analyses (i.e. modelling) conducted.
- Summary = Represents TFL related to any summaries (i.e. descriptive statistics) of the observed raw data.
- Individual = Represents FL related to any displays of individual subject observed raw data.

[1] Forest plots

[2] Only for prior ESA use and baseline Hgb.

7.2.2. Summary Measure

Number (%) of Subjects with Mean Hgb in Target Range during the Primary Efficacy Evaluation Period

The number and percentage of responders, who are subjects with observed mean Hgb within the target range during the primary efficacy evaluation period, and non-responders will be summarized. Odds ratio will be estimated by using a logistic regression and provided along with its 95% CI and superiority one-sided p-value. Analysis will be repeated by the ITT, PP, and Efficacy ND populations in the same manner. The subgroup analysis based on the mITT population will be also produced using tables and a forest plot. For the Efficacy PD population, the summary of the number and percentage of responders and non-responders will be produced and the summary by prior ESA use and baseline Hgb will be created.

7.2.3. Population of Interest

The principal secondary efficacy analyses will be based on the mITT population, unless otherwise specified.

7.2.4. Strategy for Intercurrent (Post-Randomization) Events

Intercurrent events	Strategy
Study withdrawal	The occurrence of the event is taken to be a component of response to treatment. If a subject has no available Hgb data during Week 40 to 52 due to early withdrawal, the subject is deemed as a non-responder. If a subject has at least one available Hgb data during Week 40 to 52, a response to treatment will be defined by whether the mean Hgb during Week 40 to 52 using observed Hgb values within target range.
Prohibited medications (except for commercial ESA medications)	Basically, the occurrence of the event is taken to be irrelevant. Subjects with long-term use of prohibited medications will be excluded from PP population.
Blood transfusion and/or commercial ESA medication	The occurrence of the event is taken to be irrelevant.
Intermittent missing	The occurrence of the event is taken to be irrelevant.

7.2.5. Statistical Analyses / Methods

Details of the planned displays are provided in [Appendix 10: List of Data Displays](#) and will be based on GSK data standards and statistical principles.

Unless otherwise specified, endpoints / variables defined in Section 7.2.1 will be summarised using descriptive statistics, graphically presented (where appropriate) and listed.

7.2.5.1. Statistical Methodology Specification

Endpoint / Variables

 Number (%) of subjects with mean Hgb in the target range (11.0-13.0 g/dL) during the primary efficacy evaluation period (Week 40 to 52)
Model Specification

 The percentage of subjects with observed mean Hgb during the primary efficacy evaluation period within target range will be derived from the mean of observed Hgb values during the primary efficacy evaluation period for individuals. Analyses will be conducted by a logistic regression model as follows: $\text{logit}(\pi) = \beta_0 + \beta_{\text{baseline}} * \text{Baseline}_i + \beta_j + \beta_l + \varepsilon$ 
 π_i: treatment success (mean(Hgb_i) is within the target range or not) β_0: Intercept β_{baseline}: baseline Hgb effect Baseline_i: Hgb measurement for subject i β_j: treatment effect (j= daprodustat, epoetin beta pegol) β_l: Prior ESA use effect (l = ESA user, ESA non user) ε: random error i: subject (i = PPD ..., N) N: number of subjects included in the analysis The mean Hgb during the primary efficacy evaluation period will be calculated by individuals and confirmed if the values are in the target range or not. Therefore, subjects who have at least one Hgb measurement during the evaluation period will be included in this analysis. A subject who has missing data of the mean Hgb during the primary efficacy evaluation period due to intercurrent events will be regarded as a non-responder. The odds ratio (daprodustat/epoetin beta pegol) will be obtained as follows: $\text{OR} = \exp(\beta_{\text{daprodustat}} - \beta_{\text{epoetin}})$ The odds ratio, the Wald-type 95% CI. and a superiority one-sided p-value based on a z-score will be provided together.
Model Checking & Diagnostics

 If the logistic regression cannot be applicable due to all responders or all non-responders, the odds ratio and the associated statistics will not be provided. If there is a problem with quasi-complete separation, a penalized likelihood method by Firth will be used by specifying the FIRTH option in the MODEL statement.

Model Results Presentation

- The superiority assessment will be performed only if the primary endpoint achieved non-inferiority.
- The number and percentage of subjects with observed mean Hgb during the primary efficacy evaluation period within the target range (11.0-13.0 g/dL) will be presented by treatment group. If available, the odds ratio (daprodustat/epoetin beta pegol), the associate 95% CI, and a superiority one-sided p-value will also be provided, otherwise 'NC'(not calculated) will be provided for odds ratios and the associated statistics.
- Superiority will be established if the lower limit of the 95% CI for the odds ratio is greater than 1.0 (i.e. a p-value is smaller than 0.025).

Subgroup Analyses

- The subgroup analyses will be based on the mITT population for all subgroup specified in Section 5.4.2 and the Efficacy PD population for baseline Hgb.
- The statistical analysis method uses the same logistic model, unless the logistic model is not applicable due to all responders or all non-responders.
- Graphical summaries for odd ratios and the associated 95% CIs will be produced using a forest plot for the mITT population. If the logistic model is not applicable, 'NC'(not calculated) label will be provided.

Sensitivity and Supplementary Analyses

- The mITT Population will be used for this logistic analysis, and the supplementary analysis using same logistic model will be repeated in the ITT and PP Population to evaluate the robustness of the conclusion. In the ITT population, subjects who have no available Hgb after Week 40 will be considered as non-responder.
- The logistic regression will be performed by a set of pre-specified subgroups (Section 5.4.2). These subgroup analyses are considered exploratory to assess for consistency with the overall results.

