modified ITT (mITT)	
 Consist of all ITT subjects who have at least one Hgb measurement during the efficacy evaluation period. Subjects will be analyzed according to randomized treatment. This population will be the primary population for an assessment of superiority. 	
 Study Population Efficacy
Per-Protocol (PP)	
 Consists of all mITT subjects who are not major protocol violators. This population will be used for efficacy sensitivity analyses. Protocol deviations that would exclude subjects from the PP population are defined in Section 4.1(Protocol Deviations) and Appendix 1: Protocol Deviation Management and Definitions for Per Protocol Population. 	
 Efficacy
Pharmacokinetic (PK)	
 Consists of all GSK1278863-treated subjects from whom PK samples are collected and analyzed. 	
 PK

NOTES :

- Basically, enrolled population will be the same as randomized population because a subject is going to be given randomized number as soon as passed screening.
- Refer to [Appendix 10](#): List of Data Displays which details the population used for each display.
- Refer to [15.6.2](#) for handling rescreened subjects.

[1]: Only subjects receiving incorrect randomized treatment for the duration of their study participation will be analyzed according to the treatment received. Otherwise, subjects will be analyzed according to the treatment to which they were randomized.

Figure 1 Analysis Populations

NOTES :

- [1]: Subjects who never passed screening even if rescreened
- [2]: Subjects who are not given randomization number
- [3]: Subjects who never receive study treatment
- [4]: Subjects who do not have Hgb measurement at both baseline and at least one scheduled visits following the baseline
- [5]: ESA non-users in Cohort 1 subjects
- [6]: Subjects who have no Hgb measurement during the efficacy evaluation period
- [7]: Subjects who are major protocol violators (See Section 4.1 and [Appendix 1](#))

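### The confirmatory superiority test runs in mITT, so early withdrawals whom the SAP calls non-responders are left out of it and are counted as such only in the supplementary ITT analysis

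*SAP*

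**What the plan says.** **Population.** SAP Section 4 defines mITT as follows: "Consist of all ITT subjects who have at least one Hgb measurement during the efficacy evaluation period". It adds: "This population will be the primary population for an assessment of superiority". The notes to Figure 1 name the group removed in going from ITT to mITT: "Subjects who have no Hgb measurement during the efficacy evaluation period". Section 7.2.3 agrees: "The principal secondary efficacy analyses will be based on the mITT population, unless otherwise specified".

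**Strategy for withdrawal.** Section 7.2.4 treats study withdrawal as part of the response definition: "If a subject has no available Hgb data during Week 40 to 52 due to early withdrawal, the subject is deemed as a non-responder". This is a composite strategy.

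**Model specification.** Section 7.2.5.1 puts two rules next to each other. The inclusion rule is "Therefore, subjects who have at least one Hgb measurement during the evaluation period will be included in this analysis". The sentence after it classes as a non-responder anyone whose evaluation-period mean is missing because of an intercurrent event.

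**Supplementary analysis.** The same section repeats the logistic model in ITT and PP, and says: "In the ITT population, subjects who have no available Hgb after Week 40 will be considered as non-responder". The ITT run is listed as Table 2.26.

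**Decision rule.** Superiority is declared if the lower 95% confidence limit of the odds ratio exceeds 1.0, equivalent to a one-sided p-value below 0.025. The test is reached only after non-inferiority is shown (Sections 2.4, 5.5 and 7.2.5.1).

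**The concern.** The composite rule and the confirmatory population do not fit together. The subjects to be counted as failures are the ones mITT removes. A reader of Section 7.2.4 would take the superiority result to penalise early withdrawal, but the planned test ignores it.

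The test as planned compares in-range proportions among subjects who have Hgb data in Weeks 40 to 52. That group is selected after randomization, in an open-label trial. If withdrawal differs between arms, or is related to failure or intolerance, the comparison no longer rests on randomization alone and does not estimate what Section 7.2.4 describes. The primary non-inferiority analysis is not affected.

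**Working it through.** **Step 1: can the non-responder rule act inside mITT?** Each of Weeks 40, 44, 48 and 52 is either observed or missing, which gives 2^4 = 16 patterns. The individual mean uses whatever values are observed, so it is missing in only one pattern, with all four visits missing. mITT requires at least one value, so that pattern is outside it. Patterns inside mITT with a missing mean: 0. Patterns in ITT with a missing mean: 1. The two adjacent rules in Section 7.2.5.1 therefore cannot both operate in the confirmatory analysis.

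**Step 2: what can it change?** The SAP states no response rate, withdrawal rate or power for this endpoint, so there is no figure to reproduce. What follows is illustration.

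Inputs from the SAP:
- about 286 non-dialysis subjects (Section 2.3) randomized 1:1, so 286 / 2 = 143 per arm; the actual ITT is smaller because Cohort 1 ESA non-users are left out
- one-sided significance level 0.025

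Assumptions:
- in-range rates among observed subjects of 85% vs 75%, with 90% vs 80% as a second case (daprodustat first)
- 0 to 20% with no Week 40-52 Hgb
- an unadjusted odds ratio, whereas the SAP's model adjusts for baseline Hgb and prior ESA use

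With a of n1 responders on daprodustat and c of n2 on epoetin beta pegol:
- OR = [a/(n1 − a)] / [c/(n2 − c)]
- SE(ln OR) = √[1/a + 1/(n1 − a) + 1/c + 1/(n2 − c)]
- z = ln OR / SE; one-sided p = 1 − Φ(z)

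Worked case, 10% withdrawn in each arm, 85% vs 75%: 143 × 0.90 ≈ 129 observed per arm, with 129 × 0.85 ≈ 110 and 129 × 0.75 ≈ 97 in range.
- mITT: OR = (110/19)/(97/32) = 1.91; SE = √(1/110 + 1/19 + 1/97 + 1/32) = 0.321; z = 2.01; p = 0.022; lower limit 1.02. Superiority is declared.
- Withdrawals as non-responders: OR = (110/33)/(97/46) = 1.58; SE = 0.267; z = 1.71; p = 0.043; lower limit 0.94. Superiority is not declared.

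Other cases at 85% vs 75%:

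| Withdrawn | mITT counts | mITT OR, p | Non-responder counts | OR, p |
|---|---|---|---|---|
| 0% / 0% | 122/143 vs 107/143 | 1.95, 0.014 | same | 1.95, 0.014 |
| 10% / 10% | 110/129 vs 97/129 | 1.91, 0.022 | 110/143 vs 97/143 | 1.58, 0.043 |
| 15% / 5% | 104/122 vs 102/136 | 1.93, 0.021 | 104/143 vs 102/143 | 1.07, 0.40 |
| 10% / 20% | 110/129 vs 86/114 | 1.88, 0.028 | 110/143 vs 86/143 | 2.21, 0.001 |

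At 90% vs 80%, p moves from 0.013 to 0.036 (10% / 10%), from 0.014 to 0.44 (15% / 5%) and from 0.015 to 0.0006 (10% / 20%).

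**The case against.** - **The rule is used somewhere.** A reader might infer that the composite strategy is never applied. That is not so: Section 7.2.5.1 applies it in the supplementary ITT regression, and it could also act in the Efficacy ND run listed in Section 7.2.1. This stands and limits the point to the confirmatory test. A supplementary table does not decide the superiority claim.
- **mITT is a deliberate choice.** It is named consistently for superiority, and Table 1 of the SAP lists no departure from the protocol on it, so it may be inherited. Choosing mITT is not in itself an error. The defect is that the population and the stated strategy disagree, and either could be changed.
- **The numbers are assumed, and part of the shift is not bias.** This stands. With equal withdrawal, the change in p comes from asking a different question and does not show bias. With 10% vs 20% withdrawn, mITT is the less favourable analysis. A reader might infer that mITT favours daprodustat; the document does not support any direction.
- **The Hgb flowchart in Section 15.6.3 is not visible.** If it restricts the mean to on-therapy values, a subject whose only Week 40-52 value is off-therapy might be in mITT with a missing mean. That would not bring in withdrawals with no Hgb at all.

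**Conclusion.** The point holds for the confirmatory test. Sections 4, 7.2.3 and 7.2.5.1 run it in mITT, while Sections 7.2.4 and 7.2.5.1 call subjects lost before Week 40 non-responders. Those subjects are outside mITT, so the rule reclassifies none of them where the superiority claim is decided. The test estimates an odds ratio among subjects with Week 40-52 Hgb, which is not the quantity Section 7.2.4 describes. This follows from the wording alone and needs no assumed rates.

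The size does depend on assumptions. Under the illustrative rates, the choice of analysis can turn success into failure or failure into success. With no withdrawal before Week 40 the two analyses are identical.

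**What to change.** **Preferred.**
- In Sections 4, 7.2.1, 7.2.3 and 7.2.5.1, name the ITT logistic regression with withdrawals as non-responders (Table 2.26) as the confirmatory superiority analysis, with mITT as supportive.
- In Section 7.2.5.1, delete the sentence limiting inclusion to subjects with an evaluation-period Hgb. In the ITT sentence, replace the reference to after Week 40 with Weeks 40 to 52; read literally, the present wording leaves a subject whose only value is at Week 40 unclear.
- State that the rule covers every subject with no Week 40-52 Hgb, whatever the reason. Section 7.2.4 now ties it to early withdrawal and calls intermittent missing data irrelevant, so a subject who stays in the study but has no value at all four visits is not clearly classified.
- Add Table 2.26 to the headline set, which now carries only the mITT Table 2.25 for this endpoint, and align the mITT subgroup displays (Table 2.29 and Figure 2.21).
- Record the change in Table 1 if the protocol names mITT.

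**Minimum, if mITT stays confirmatory.** Rewrite Section 7.2.4 and the non-responder sentence in Section 7.2.5.1 to say that the test concerns the in-range proportion among subjects with Week 40-52 Hgb.

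**Cost.** SAP wording and some re-targeted displays; the ITT table is already planned. Where subjects lack Week 40-52 Hgb, response rates will look lower, and the superiority result may become less or more favourable.

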7. EFFICACY ANALYSES

7.1. Primary Efficacy Analyses

7.1.1. Endpoint / Variables

[Endpoint / Parameter/ Display Type]	Populati on	Absolute						
		Stats Analysis			Summary		Individual	
		T	F	L	T	F	F	L
Mean Hgb based on observed Hgb during the Primary Efficacy Evaluation Period (i.e. Individual Mean of Hgb at Week 40, 44, 48, and 52)								
(Preliminary assessment) Observed Case	mITT				Y			
Observed Case	Efficacy PD				Y			
Observed Case by Subgroup ^[3]	Efficacy PD				Y			
Model based Mean Hgb during the Primary Efficacy Evaluation Period								
(Primary) MMRM	ITT	Y	Y					
MMRM	mITT/PP /Efficacy ND	Y	Y					
MMRM By Subgroup	ITT	Y	Y ^{[1][2]}					
MMRM Excluding ESA Users with Hgb rapid increase at Week 2	ITT	Y	Y					
MMRM Evaluable Hgb	ITT	Y	Y					
Analysis of Covariance (ANCOVA)	mITT/PP	Y						
ANCOVA By Subgroup	mITT	Y	Y ^[1]					
Tipping Point Analysis	ITT/mITT /PP	Y	Y					

NOTES :

- T = Table, F = Figure, L = Listing, Y = Yes display generated.
- Stats Analysis = Represents TFL related to any formal statistical analyses (i.e. modelling) conducted.
- Summary = Represents TFL related to any summaries (i.e. descriptive statistics) of the observed raw data.
- Individual = Represents FL related to any displays of individual subject observed raw data.

[1] Forest Plots

[2] For prior ESA use, Hgb curve over time will also be displayed.

[3] Only for prior ESA use and baseline Hgb.

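### Read literally, the supplementary ITT responder rule leaves out the Week 40 visit and so does not match the endpoint's own non-responder rule

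*SAP*

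**What the plan says.** The principal secondary endpoint is whether a subject's mean Hgb in the primary efficacy evaluation period lies within 11.0 to 13.0 g/dL. Section 7.1.1 describes that mean as the "Individual Mean of Hgb at Week 40, 44, 48, and 52", so Week 40 is one of its four visits.

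Four places in the SAP treat missing evaluation-period data in the same way:

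- Section 7.2.4, on withdrawal: "If a subject has no available Hgb data during Week 40 to 52 due to early withdrawal, the subject is deemed as a non-responder".
- Section 7.2.4, on partial data: "If a subject has at least one available Hgb data during Week 40 to 52, a response to treatment will be defined". The test is then whether the average of the observed values is in range.
- Section 7.2.5.1, model specification: "subjects who have at least one Hgb measurement during the evaluation period will be included in this analysis".
- Section 4, mITT: "Consist of all ITT subjects who have at least one Hgb measurement during the efficacy evaluation period".

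Section 7.2.2 adds: "Analysis will be repeated by the ITT, PP, and Efficacy ND populations in the same manner".

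The last block of Section 7.2.5.1, on sensitivity and supplementary analyses, then gives a rule for the ITT repeat alone: "In the ITT population, subjects who have no available Hgb after Week 40 will be considered as non-responder".

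**The concern.** The ITT sentence uses a different trigger from the rest of the endpoint definition. Elsewhere the test is whether any Hgb exists in Weeks 40 to 52, with Week 40 included. Here it is whether any exists after Week 40. Taken at its word, it disregards a Week 40 value that stands alone.

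The ITT repeat is there to show whether the mITT result holds once subjects with no evaluation-period data are counted as failures. Since mITT is a subset of ITT, the two analyses should differ only through those added subjects. Under the literal wording, a subject already classified as a responder in mITT could also change status, and part of any difference between the two results would come from the phrasing. The Efficacy ND repeat has no special sentence, so the Section 7.2.4 rule applies there. The same subject could then be a responder in Table 2.25 (mITT), a non-responder in Table 2.26 (ITT) and a responder again in Table 2.28 (Efficacy ND).

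**Working it through.** The SAP gives no figure for this analysis, so there is none to reproduce. The check applies both rules to test subjects and then sizes the effect under stated assumptions.

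**1. The two rules side by side**

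- Rule A (Section 7.2.4): non-responder if there is no Hgb in Weeks 40 to 52; otherwise the observed mean decides.
- Rule B (ITT sentence in 7.2.5.1, read literally and counting only scheduled visits): non-responder if there is no Hgb at Week 44, 48 or 52; otherwise the observed mean decides.

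| Hgb available in the evaluation period | In mITT? | Rule A | Rule B |
|---|---|---|---|
| Week 40 only, 11.8 g/dL | yes | responder | non-responder |
| Week 40 only, 10.2 g/dL | yes | non-responder | non-responder |
| None | no | non-responder | non-responder |
| Week 44 only, 12.0 g/dL | yes | responder | responder |

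Only the first kind of subject changes status.

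**2. How the SAP words boundaries elsewhere.** Section 7.1.6.2 refers to events on or after Week 40, and Section 7.1.6.3 uses the same inclusive form for Week 4. A programmer could therefore fairly read the ITT sentence as exclusive.

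**3. How many subjects.** The withdrawal rate and the proportion in range are assumptions. The base of about 286 is the planned ND size in Section 2.3.

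- Share whose last scheduled value is Week 40 = withdrawal rate × 4/52, if withdrawals are spread evenly over 52 weeks.
- At 10%: 0.10 × 4/52 = 0.8%, and 286 × 0.10 × 4/52 = 2.2 subjects.
- At 25%: 0.25 × 4/52 = 1.9%, and 286 × 0.25 × 4/52 = 5.5 subjects.
- With 75% in range: 2.2 × 0.75 = 1.7 and 5.5 × 0.75 = 4.1, or about 2 to 4 subjects in total.

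**4. Effect on the odds ratio.** This is an unadjusted 2×2 illustration with 143 per arm and assumed response rates. OR = x1(n − x2) / [(n − x1)x2], with a Wald 95% lower limit.

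- 75% vs 60%, none reclassified: x1 = 107, x2 = 86, OR 1.97, lower limit 1.19.
- 75% vs 60%, two reclassified in each arm: x1 = 105, x2 = 84, OR 1.94, lower limit 1.18.
- 80% vs 70%, none reclassified: OR 1.69, lower limit 0.98.
- 80% vs 70%, two reclassified in each arm: OR 1.66, lower limit 0.97.

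With the reclassified subjects balanced across arms, the result barely moves.

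**The case against.** The strongest reply is that the sentence was never meant to alter the response rule. Section 7.2.2 says the repeats follow the same manner, and Section 7.2.5.1 says they use the same model. Note 6 to Figure 1 in Section 4 describes the subjects who are in ITT but not in mITT as those without an Hgb measurement in the efficacy evaluation period. On that reading the ITT sentence only says what happens to those subjects, and nobody changes status. The SAP is also loose at boundaries elsewhere: Section 15.6.6 names a fall in eGFR of 30% or more but codes it as strictly below −30%. This is probably the intent. It does not make the sentence correct as written, and it is the only rule specific to ITT.

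A second reply is that even the literal trigger may seldom fire. Appendix 2 schedules hematology at early withdrawal and again at follow-up, four weeks after withdrawal. A subject who leaves soon after Week 40 would often have an Hgb dated after Week 40, and the sentence does not restrict which values count as available. Section 15.6.3 also substitutes a HemoCue value when the central laboratory value for a visit is missing. Both points stand, so the count above is better read as an upper range.

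A reader might infer that the wording could overturn the superiority finding. One-sided scenarios that cross 1.0 can be built: at 75% vs 60%, six reclassified in the daprodustat arm alone bring the lower limit to 0.97; at 80% vs 70%, four in the comparator arm alone bring it to 1.13. The documents do not support that inference. Nothing in the SAP suggests that such subjects would fall in one arm, the rates are assumed, and superiority is decided in mITT.

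**Conclusion.** The point holds as a small wrong-as-written rule. The ITT trigger in Section 7.2.5.1 does not agree with Section 7.2.4, with the model specification in the same section, or with the mITT definition. Read literally, it can make one kind of subject, with a lone in-range Week 40 Hgb and no later available value, a responder in mITT and a non-responder in ITT.

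The number affected is likely to be a handful at most. That rests on assumed withdrawal and in-range rates, on even withdrawal over time, and on a base of 286 that exceeds the ITT population if any Cohort 1 ESA non-users or subjects without post-baseline Hgb were randomized. Only the supplementary ITT repeat is affected. The confirmatory mITT test, the testing order and type I error control are unchanged.

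**What to change.** Reword the ITT sentence in Section 7.2.5.1 so that a subject counts as a non-responder for missing data only when no Hgb is available during the primary efficacy evaluation period, naming the Week 40, 44, 48 and 52 visits. Naming the visits restores Week 40 and also settles that early-withdrawal and follow-up values do not bear on the rule. ITT then differs from mITT only by adding subjects with no evaluation-period value.

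The cost is one phrase in the SAP. It needs no new data and no additional analysis.
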